6.4 SUBJECT SETS ANALYSED

The following analysis sets will be defined for this trial:

Enrolled Set (ES)

This patient set includes all patients who signed informed consent. It will be used for analyses of patient disposition.

Safety Analysis Set (SAF):

This patient set includes all patients who received at least one dose of study drug in trial 1368-0067. This is the main analysis set for efficacy and safety. Patients will be analyzed according to the actual treatment received.

Safety Set ADA (SAF-ADA)

This patient set includes all patients who received at least one dose of study drug and had at least one evaluable ADA sample in trial 1368-0067. This is the main analysis set for ADA impact on efficacy and safety. Patients will be analyzed according to the actual treatment received.

The discussion of all exceptional cases and problems and the decisions on the allocation of patients to populations will be made at the RPM/DBLM at the latest.

Table 6.4: 1 Overview of use of patient analysis sets by class of endpoint and handling of estimand and missing data

Class of endpoint	
	ES SAF
Disposition	OR
Compliance and exposure	OR
iPD	OR
Demographic/baseline characteristics	OR
Concomitant medication	OR
Primary endpoint	OR
Secondary binary efficacy endpoints	OC-NRI: for binary efficacy endpoints
Secondary continuous efficacy endpoints	OC for continuous efficacy endpoints.
Further efficacy endpoints	OC for continuous efficacy endpoints. OC-NRI: for binary efficacy endpoints
Plasma concentration & ADA	OR
Efficacy endpoints by ADA impact	OC for continuous efficacy endpoints OC-NRI for binary efficacy endpoints
AE	OR
Lab data, vital signs	OC-IR

For explanation of the different approaches with regard to missing data see [Section 6.6](#).

[figure not shown]
OC = observed cases excluding values after any use of rescue medication.

OC-IR = observed cases including also values after any use of rescue medication.

OC-NRI = values after any use of rescue medication will be censored and impute with non-responder..

OR = original results.

NRI = Non-Response Imputation, cf. [Section 6.6.2](#).

6.6 HANDLING OF MISSING DATA AND OUTLIERS

Section 7.3 of the CTP describes the handling of missing data.

The original results (OR) approach implies the presentation of data exactly as observed (not using time windows and not setting values to missing).

OR analysis will be performed on parameters and endpoints that are either not affected by patients' rescue therapy use (e.g., plasma concentration level of spesolimab, rescue therapy itself), or, it is not meaningful to apply any imputation rule for the replacement of missing values.

6.6.1 Withdrawals

The reasons for withdrawal from treatment will be reported as indicated on the eCRF.

6.6.2 Efficacy data

Based on the different reasons for patients' data missing for different endpoints, various approaches will be used to assess the impact of missing data on the efficacy endpoints of this trial, depending upon the type of the endpoint (cf. [Table 6.4: 1](#)) Approaches to be applied are described below.

Missing data imputations will be performed using all available on-treatment data observed up to the respective analysis cut-off date, if applicable.

Some efficacy endpoints are defined with a particular binary outcome, i.e. Achievement of PGA score of 0 or 1. Then imputation is planned to take place only at the binary level, i.e., the

PGA score itself as a ordinal variable will not be imputed, but the binary endpoints derived based on these scores will be imputed, unless otherwise specified.

Continuous efficacy endpoints

For interim analysis planned at week [REDACTED] those efficacy endpoints up to Week [REDACTED] which are continuous in nature, the use of a restricted maximum likelihood (REML)-based mixed effect model with repeated measures (MMRM) approach, if applicable, will ensure that missing data are handled implicitly, via a missing at random assumption, by the statistical model.

For final analysis, the efficacy endpoints during on-treatment period will be displayed descriptively using following methods:

- Observed cases (OC) approach will include all collected data, without imputation for any missing data. Such an OC approach will exclude all values measured after intake of a rescue therapy.

Binary efficacy endpoints

For all binary endpoints (i.e. endpoints that are either 1 (patient responded) or 0 (patient did not respond)), the following will be performed as the primary imputation approach (analysis type: No Response Imputation [NRI]):

- If there are data at visits both before and after the visit with a missing outcome, then impute as success only if both neighbouring visits also represent a success (independent of whether the preceding and following observations were selected for analysis based on time windows described in [Section 6.7](#) and no rescue treatment has been given during this period);
- Otherwise, impute as a failure.

OC-NRI method will be used to display the binary data.

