3.3.4.1 Discontinuation of trial treatment

An individual patient will discontinue trial treatment if:

- The patient wants to discontinue trial treatment, without the need to justify the decision.
- The patient has repeatedly shown to be non-compliant with important trial procedures and, in the opinion of both, the investigator and sponsor representative, is not willing or able to adhere to the trial requirements in the future.

- The patient develops infections such as HIV, viral hepatitis or tuberculosis. However, if latent tuberculosis is diagnosed during the trial, patients can receive anti-tuberculosis treatment as per investigator discretion and continue receiving study medication as per investigator. Refer to [Section 6.2.1.2](#)
- The patient needs to take concomitant medication such as immunosuppressive biologics, live vaccines, or other concomitant medication that interferes with the Investigational Medicinal Products (IMP) or other trial treatment. Also refer to [Sections 4.2.1](#) and [4.2.2](#).
- The patient can no longer receive trial treatment for medical reasons such as surgery, serious or severe Drug Induced Liver Injury attributable to the trial drug, other adverse events, other diseases, or pregnancy. Also refer to [Sections 5.2.6.1.4](#) and [5.2.6.2.3](#).
- The patient develops suicidal ideation of type 4 or 5 in the C-SSRS (i.e. active suicidal thoughts with method and intent but without specific plan, or active suicidal thoughts with method, intent and plan) or any suicidal behaviour (i.e. actual attempt, interrupted attempt, aborted attempt, or preparatory acts or behaviour). The patient should immediately be referred to a mental health professional for further work-up.
- The patient is a Non-responder on 1200 mg of IMP and there is no change or no improvement in their HS-PGA grade at Week 24 compared to Week 12.

In addition, the principal investigator may discontinue subjects at any time based on his or her clinical judgment.

For individual stopping rules related to specific AEs, please see [Section 4.2.1](#).

In case of a temporary reason, trial treatment should be restarted if medically justified, please see [Section 4.1.4](#).

For all patients the reason for withdrawal from trial treatment (e.g. adverse events) must be recorded in the CRF. This data will be included in the trial database and reported.

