7.2.3 Secondary endpoint analyses

For binary endpoints, the efficacy data will be presented over time based on SAF where any data collected after the use of rescue therapy will be censored and then imputed using the Non Response Imputation (NRI) method as described in [Section 7.3](#).

For continuous endpoints, the efficacy data will be presented over time based on SAF where any data collected after the use of rescue therapy will be censored and then may be handled by a mixed effect model for repeated measurements (MMRM).

Further, it is also of interest to explore week 12 efficacy performance of patients who were responders, partial responders and non-responders in the 1368-0052 trial respectively as defined in [Table 3.1: 1](#).

Further details will be provided in the TSAP.

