7.3 HANDLING OF MISSING DATA

Every effort will be made to collect complete data at all visits. However, missing data will still occur and approaches to handle this are proposed below.

For the safety data, including the primary endpoint, no missing data imputations are planned.

For secondary binary efficacy endpoints, a NRI approach will be applied to the missing visits; that is, imputing as a failure to achieve a response in the visits with missing endpoint score, however:

- If there are visits with available data both before and after the visit with a missing outcome, then impute as a success only if both the preceding and the following measurement indicate success and no rescue medication has been given during this period.
- Otherwise, impute as a failure to achieve a response (i.e. no response imputation).

For secondary continuous efficacy endpoints, MMRM method may be applied to handle the missing data.

Further analyses to assess the robustness of the results on efficacy endpoint will be described in the TSAP if necessary.

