6.3 INTERCURRENT EVENTS

The expected intercurrent events (ICEs) of interest in this trial are:

- Use of rescue therapy (while still on treatment), as defined in [Section 5.4.3](#)
- Treatment discontinuation without restricted medication, flagged by medical review if occurring
- Treatment discontinuation with restricted medication, flagged by medical review if occurring

The strategies for handling intercurrent events in this trial are as follows:

Hybrid Strategy (EC-H): All intercurrent events except for the administration of rescue therapy will be handled using the treatment policy approach. Rescue therapy will be handled

using the hypothetical approach, under the scenario in which the intercurrent event would not occur. This will be used as the **primary strategy** of implementing the Estimand Concept (EC), allowing the effects of adherence, i.e., regardless of treatment discontinuation, but excluding the effects of rescue therapy.

No deaths are expected in this trial. In the unlikely event of a death occurring, it will be handled using a hypothetical approach for each strategy.

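### At the final analysis, continuous efficacy endpoints are shown only as observed cases, so means after Week 12 describe patients still unrescued and observed rather than the declared hybrid estimand

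*SAP*

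**What the plan says.** **Estimand.** SAP 6.3 handles rescue "using the hypothetical approach, under the scenario in which the intercurrent event would not occur". Other intercurrent events, death apart, follow treatment policy. SAP 7.5.2 says the continuous secondary endpoints implement this hybrid, and SAP 7.6.1 says the same of the further endpoints. SAP 7.5.2 then censors data after the intercurrent event without restricting this to rescue.

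**Final analysis.** SAP 6.6.2: "Observed cases (OC) approach will include all collected data, without imputation for any missing data", and "Such an OC approach will exclude all values measured after intake of a rescue therapy". Table 6.4:1 in SAP 6.4 agrees: "OC = observed cases excluding values after any use of rescue medication". Binary endpoints instead receive non-response imputation.

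**Interim.** SAP 3 places it when all patients have reached Week 12. For that analysis only, SAP 6.6.2 plans a REML MMRM, where applicable, which "will ensure that missing data are handled implicitly, via a missing at random assumption, by the statistical model".

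**Protocol.** Section 7.3: "For secondary continuous efficacy endpoints, MMRM method may be applied to handle the missing data". Section 7.2.3 is similar. Neither limits the model to an interim, and SAP 4 does not list its absence from the final analysis as a change.

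**Routes out of the data.** Rescue is treatment for disease worsening, defined in protocol 4.2.2.2 as a 150% increase in abscess and inflammatory nodule (AN) count. Systemic antibiotics for worsening are allowed after Week 12 (4.2.2.3). Under 3.3.4.1 and Table 3.1:1, an up-titrated Non-responder stops treatment if "there is no change or no improvement in their HS-PGA grade at Week 24 compared to Week 12".

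**The concern.** Deleting post-rescue values does not estimate what those values would have been without rescue. It leaves a mean over patients who are unrescued and still measured at that visit. Both routes out follow poor response and operate mainly after Week 12, which is where the planned model ends.

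Protocol 3.2 and 4.1.2 set out to learn whether response is sustained, including on the reduced dose. A late OC mean cannot separate sustained response from a change in who is left. The two endpoint types also treat the same patient in opposite ways: after rescue, the patient is a failure for HiSCR but drops out of the mean AN change from which HiSCR is largely derived.

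**Working it through.** **1. Nothing to reproduce.** Protocol 7.5 makes no sample-size calculation, and neither document states an SD, a rescue rate or a discontinuation rate. Size can only be shown under assumptions.

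**2. Identity.** Let f be the share gone. The full-set mean is (1 - f) x mean(remaining) + f x mean(gone). Hence

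OC mean - full-set mean = f x [mean(remaining) - mean(gone)].

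With about 45 patients (protocol synopsis):
- 9 of 45 gone (f = 0.20), those remaining 40 points better: 0.20 x (-40) = -8 points.
- 18 of 45 gone (f = 0.40), those remaining 60 points better: 0.40 x (-60) = -24 points.
- No gap: 0, whatever f is.

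**3. Simulation.** Assumptions: 45 patients; normal AN percent change with true mean -30% from Week 12 to Week 98; SD 40, 60 or 90; correlation parameter 0.4 or 0.8 at a 24-week lag; 800 replicates per setting. From Week 12, a recorded change above +150% leads to rescue with probability 0.7. The stand-in for the Week 24 stop removes patients whose Week 12 change is worse than -25% and who improve by less than 5 points by Week 24. Error is the full-set mean minus the OC mean at Week 98, so positive is too favourable.

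| SD | Corr. | Rescue + Week 24 exit: gone | OC mean | Error | Rescue alone: gone | OC mean | Error |
|---|---|---|---|---|---|---|---|
| 40 | 0.4 | 16% | -32.30 | 2.25 | 0% | -30.29 | 0.01 |
| 40 | 0.8 | 22% | -37.75 | 7.75 | 0% | -30.02 | 0.00 |
| 60 | 0.4 | 17% | -33.33 | 3.56 | 0% | -30.41 | 0.22 |
| 60 | 0.8 | 22% | -41.21 | 11.82 | 0% | -29.69 | 0.43 |
| 90 | 0.4 | 20% | -37.45 | 7.43 | 5% | -33.22 | 3.11 |
| 90 | 0.8 | 23% | -49.49 | 19.99 | 4% | -36.22 | 6.52 |

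At Week 12 the OC mean is within about 1 point of -30 in every row. When 30% leave for reasons unrelated to outcome (SD 50, correlation 0.6), the Week 98 OC mean is -29.7, so there is no drift.

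**4. What a likelihood method does.** A missing-at-random (MAR) estimate by sequential regression on earlier visits, standing in for MMRM, gives -29.2 to -30.3 at Week 98 across the table. This is a best case, because exits here depend only on recorded values of the same endpoint.

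**5. Limits.** The Week 24 stand-in is not the protocol's rule, which applies to parent-trial Non-responders who were up-titrated and is judged on HS-PGA. The normal model allows changes below -100%, which a count cannot show, so the largest errors are rough.

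**6. Treatment-policy part.** After stopping, lesion counts are scheduled only at EoT and the two-week follow-up, not at EoS (Flow Chart from Week 14). Few post-discontinuation values will exist, and SAP 7.5.2 read literally would censor even those.

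**The case against.** **Tempting stronger readings.** A reader might infer that every continuous secondary endpoint is biased over two years. The documents do not support that. The secondary horizon is redacted, and the secondary objective names a lower dose but no duration. SAP 4 adds HiSCR and NRS30 over time as further endpoints, which suggests, without proving, a shorter secondary horizon. If that horizon is Week 12, both routes out fall largely after it and the interim MMRM may already cover those endpoints.

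Nor is the SAP in breach of the protocol: the protocol's MMRM wording is permissive. Nor do all non-improving patients leave: the Week 24 rule spares Responders, Partial Responders and anyone not up-titrated, and rescued patients may stay on treatment with only their later values dropped.

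**The rest of the case.** The analysis is descriptive, with no testing. SAP 7 already gives N for each continuous summary and a cumulative table of rescue, up-titration and discontinuation; SAP 7.6.2 adds a Kaplan-Meier display of time to rescue. Some simulated errors are small against sampling error: with SD 40 the standard error is 40/sqrt(45) = 6.0 points, against an error of 2.25 in the first row.

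MMRM is no complete answer either. MAR may fail because the Week 24 stop follows HS-PGA rather than each modelled endpoint, and because counts are 12-weekly after Week 38, so worsening may go unrecorded before rescue. It would also predict stopped patients largely from continuing ones, which is not treatment policy.

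**What stands.** These points limit scope and size. They do not answer the main one: the attrition displays expose the loss but leave the means uncorrected, and a descriptive mean should still describe the quantity the SAP declares.

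**Conclusion.** The point holds for continuous efficacy displays after Week 12. The declared hybrid strategy and the only planned final method do not match, and SAP 7.5.2 conflicts with SAP 6.3 on censoring after discontinuation. The affected results are the continuous further endpoints shown over time. The four continuous secondary endpoints (AN count, draining fistula count, IHS4, HASI) join them only if their redacted horizon passes Week 12.

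Favourable drift is the likely direction, not an established result. Under the assumed inputs it is about 0 to 6.5 points with rescue at +150% alone and about 2 to 20 points with a Week 24 exit added; the actual SD and exit rates decide where it falls, and it can be near zero. No error rate is involved. What is at stake is the reading of late means, which protocol 7.2.7 expects to inform development, Investigator's Brochure updates and publications. The change should be made because it is cheap.

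**What to change.** In SAP 6.6.2, 7.5.2 and 7.6.1:

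1. At the final analysis, report the interim's REML MMRM beside the OC summary for displays after Week 12, by prior arm. Set post-rescue values to missing and keep observed post-discontinuation values within the on-treatment period.
2. Use the scheduled lesion-count visits (Flow Chart footnote 17), thinned to 12-weekly if needed, with a parsimonious covariance such as AR(1) and a random-intercept fallback. State how the unscheduled Week 24 reassessment counts enter.
3. Limit the censoring in SAP 7.5.2 to rescue, so that it agrees with SAP 6.3.
4. Label OC means as *unrescued and observed*.
5. State the MAR assumption and add one simple sensitivity analysis that departs from it, since MAR alone does not deliver the treatment-policy part for patients who stop.

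N per visit is already planned and needs no change. The cost is SAP wording and one extra model per endpoint, with no new data. The downside is possible convergence trouble with about 45 patients split by prior arm, which the thinning and the fallback are there to handle.

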6.6.3 Safety data

With respect to safety evaluations, it is not planned to impute missing values. For safety data that are displayed by time point (or visit) of measurement, the Observed cases (OC-IR: with no imputation for any missing data, which will include values after any rescue medication or treatment discontinuation.) approach will be used.

For safety data that are not displayed by visit such as AE and possibly clinically significant laboratory abnormality, original results (OR) will be used.

The only exceptions where imputation might be necessary for safety evaluation are AE dates and start and stop dates for concomitant medications. Missing or incomplete AE dates are imputed according to BI standards [\(10\)](#).

Partial start and stop dates for concomitant medications, rescue, and historical medication for HS will be imputed to enable subsequent calculation (but not for display) by the following "worst case" approach:

- If the day of the end date is missing, then the end date is set to last day of the month (or to the patient's trial completion date, if it is earlier than the last day of the month).
- If the day and month of the end date are missing then the end date is set to 31st of December of the year (or to the patient's trial completion date, if it is earlier than the 31st of December of the year).
- If the day of the start date is missing then the start date is set to first day of the month (except for rescue therapy, where the first dosing day will be used if first dosing happened in the same month).
- If the day and month of the start date are missing then the start date is set to 1st January of the year (except for rescue therapy, where the first dosing day/month will be used if first dosing happened in the same year).
- All other cases need to be assessed by the trial team on an individual basis, using the above points as guidance.

If a concomitant medication was ticked to be ongoing, it is expected that the end date is missing and will not be imputed for display purposes.

6.6.4 PK data

Missing data and outliers of PK data are handled according to BI standards ([11](#)).

6.6.5 Biomarker data

The handling of other biomarkers e.g. RNA expression will be specified in a separate document.

6.6.6 Time since first diagnosis

For incomplete information on the date of first diagnosis, time since first diagnosis will be calculated as follows:

- If the year of first diagnosis is unknown, time since first diagnosis will be set to missing.
- If day and month of the first diagnosis are unknown, time since first diagnosis will be calculated as if diagnosed on the 30th June of that year.
- If only the day of the first diagnosis is unknown, time since first diagnosis will be calculated as if diagnosed on the 15th of that month.

6.7 BASELINE, TIME WINDOWS AND CALCULATED VISITS

Measurements reported with date and time and taken prior to start of administration of trial treatment will be considered pre-treatment values. Measurements reported with a date only (and no time) and taken on the day of first administration of trial treatment will also be considered pre-treatment values. These pre-treatment values will be assigned to visits according to the nominal visit number as recorded on the eCRF or as provided by the laboratory.

Baseline, unless otherwise specified, is defined as the last measurement collected prior to the start of administration of the trial treatment.

For the baseline defined in efficacy endpoints like “change from baseline” or “compared to baseline”, unless otherwise specified, is defined as the last measurement before initiation of treatment (cf. [Section 5](#)).

Baseline for time to event endpoints, is defined as the last measurement collected prior to the start of administration of the trial treatment in the current extension trial 1368-0067.

For analysis of anti-drug antibodies (ADA), 2 different baselines will be used for the clinical trial report (CTR). For the analysis of ADA impact on pharmacokinetic (PK), the entire course of treatment is to be considered and assessments prior to initial trial of the parent trial (1368-0052) is considered baseline. Details will be discussed on the trial CTR.

For the analysis of ADA impact on safety and efficacy endpoints, baseline is defined as the first evaluable sample collected prior to treatment administration at baseline of this trial 0067.

Measurements taken after start of administration of trial treatment will be considered either on- or off-treatment values based on the definition in [Section 6.1](#), and will be assigned to visits for statistical analysis, if applicable, as defined below.

Analysis of AE data, potentially clinically significant abnormal laboratory values, concomitant medication or non-drug therapies, as well as use of rescue therapy will not be based on visits. Frequency tables for these data will be using on-treatment data and categorized based on their occurring/starting dates. Therefore, no assignment to time windows will be necessary for such data.

The derivation of the last value, minimum value and maximum value of laboratory and vital signs data will consider all on-treatment values (whether or not selected in any time window; see [Table 6.1: 1](#) for definition of the on-treatment period) within the period of interest; these will be derived for analysis of laboratory and vital signs data.

All other safety, efficacy and biomarker measurements will be assigned to visits based on extended time windows around the planned visit dates, defined relative to the day of first trial treatment (which is scheduled for Visit 2). These extended time windows are defined in [Table 6.7: 1](#), [Table 6.7:2](#), [Table 6.7:3](#).

Proprietary confidential information © 2024 Boehringer Ingelheim International GmbH or one or more of its affiliated companies.

Table 6.7: 1 Time windows for assignment of vital signs to visits for statistical analysis.

Visit number	Visit label	Planned day	Time window [day]				
			Window (per CTP)	Start (per CTP)	End (per CTP)	Start (extended)	End (extended)
1	Week0	Day1	n/a	1 ^A	1	1 ^A	1
2	Week [redacted]	Day [redacted]	+2	[redacted]			
3	Week [redacted]	Day [redacted]	+2				
4	Week [redacted]	Day [redacted]	+2				
5	Week [redacted]	Day [redacted]	+2				
6	Week [redacted]	Day [redacted]	+2				
7	Week [redacted]	Day [redacted]	+2				
8	Week [redacted]	Day [redacted]	+3				
...				
53	Week [redacted] EoT	Da [redacted]	+3	[redacted]			
54	Week [redacted] (FUP1)	Da [redacted]	+3				
55	Week [redacted] (EOS)	Da [redacted]	+10				

For patients who discontinue the treatment early and are not willing to follow the whole visit schedule:
- EOS LD^B +112 - - -

All days are counted relative to the day of first treatment of current study, which is defined as Day 1.

* For the patients who enter OLE trial, V1 is strongly recommended to be performed during the EOT of the preceding parent trial.

^A Note that measurements made at Day 1 and assigned to the on-treatment period (because mistakenly made after start of trial treatment) via assessment on date & time (i.e. safety laboratory) will not be assigned to Day 1. Such data will be listed only.

^BLD= Last dose.

Proprietary confidential information © 2024 Boehringer Ingelheim International GmbH or one or more of its affiliated companies.

Table 6.7: 2 Time windows for assignment of DLQI, PGI-S, PGI-C, HiSQoL, Pain NRS safety lab, and biomarker to visits for statistical analysis

Visit number	Visit label	Planned day	Time window [day]								
			Window (per CTP)	Start (per CTP)	End (per CTP)	Start (extended)	End (extended)				
1	Week0	Day1	n/a	1 ^A	1	1 ^A	22				
3	Week [redacted]	Day [redacted]	+2	[redacted]							
5	Week [redacted]	Day [redacted]	+2								
7	Week [redacted]	Day [redacted]	+2								
8	Week [redacted]	Day [redacted]	+3								
10	Week [redacted]	Day [redacted]	+3								
12	Week [redacted]	Day [redacted]	+3								
14	Week [redacted]	Day [redacted]	+3								
16	Week [redacted]	Day [redacted]	+3								
18	Week [redacted]	Day [redacted]	+3								
20	Week [redacted]	Day [redacted]	+3								
22	Week [redacted]	Day [redacted]	+3								
24	Week [redacted]	Day [redacted]	+3								
...					Midpoint of planned days between current visit and next visit			
52	Week [redacted]	Day [redacted]	+3								
53	Week [redacted] EoT	Day [redacted]	+3	[redacted]							
54	Week [redacted] (FUP1)	Day [redacted]	+3								
55	Week [redacted] (EOS)	Day [redacted]	+10								
For patients who discontinue the treatment early and are not willing to follow the whole visit schedule:											
-	EOS	LD ^B +112	-	-	-	-	-				

All days are counted relative to the day of first treatment of current study, which is defined as Day 1.

* For the patients who enter OLE trial, V1 is strongly recommended to be performed during the EOT of the preceding parent trial.

^A Note that measurements made at Day 1 and assigned to the on-treatment period (because mistakenly made after start of trial treatment) via assessment on date & time (i.e. safety laboratory) will not be assigned to Day 1. Such data will be listed only.

^BLD= Last dose.

Proprietary confidential information © 2024 Boehringer Ingelheim International GmbH or one or more of its affiliated companies.

Table 6.7: 3 Time windows for assignment of all the other efficacy assessments except those mentioned in [Table 6.7: 2](#) to visits for statistical analysis.

Visit number	Visit label	Planned day	Time window [day]				
			Window (per CTP)	Start (per CTP)	End (per CTP)	Start (extended)	End (extended)
1	Week0	Day1	n/a	1 ^A	1	1 ^A	1
2	Week						
3	Week						
4							

For patients who discontinue the treatment early and are not willing to follow the whole visit schedule:

- EOS LD^B +112 - - -

All days are counted relative to the day of first treatment of current study, which is defined as Day 1.

* For the patients who enter OLE trial, V1 is strongly recommended to be performed during the EOT of the preceding parent trial.

^A Note that measurements made at Day 1 and assigned to the on-treatment period (because mistakenly made after start of trial treatment) via assessment on date & time (i.e. safety laboratory) will not be assigned to Day 1. Such data will be listed only.

^BLD= Last dose.

